6.4.2 Follow-up for toxicities

Refer to Appendix 5 and Appendix 6 (Section 10.5 and Section 10.6) for the follow-up of renal events.

6.5 Continued access to study treatment after the end of the study

Not applicable

6.6 Treatment of overdose

In the event of an overdose, the Investigator should:

- Contact the medical monitor immediately.
- Evaluate the participant to determine, in consultation with Novartis medical monitor, whether study treatment should be interrupted or whether the dose should be reduced.
- Closely monitor the participant for any AE/SAE and laboratory abnormalities.
- Document the quantity of the excess dose as well as the duration of the overdose.

6.6.1 Reporting of study treatment errors including misuse/abuse

Medication errors are unintentional errors in the prescribing, dispensing, administration or monitoring of a medicine while under the control of a healthcare professional, participant or consumer (EMA definition).

Misuse refers to situations where the medicinal product is intentionally and inappropriately used not in accordance with the protocol.

Abuse corresponds to the persistent or sporadic, intentional excessive use of a medicinal product, which is accompanied by harmful physical or psychological effects.

Study treatment errors and uses outside of what is foreseen in the protocol will be recorded on the appropriate eCRF irrespective of whether or not associated with an AE/SAE. Study treatment errors and uses outside of what is foreseen in the protocol, misuse or abuse will be collected and reported in the safety database irrespective of it being associated with an AE/SAE within 24 hours of Investigator's awareness. For more information on AE and SAE definition and reporting requirements, please see the respective sections.

6.7 Concomitant and other therapy

Participants may be on a HF regimen throughout the study duration on the Investigator's discretion, except for the use of ACEI, ARBs and renin inhibitors, which are strictly prohibited. Prohibited and important concomitant medications during the conduct of the clinical trial are listed below.

6.7.1 Concomitant therapy

The Investigator must instruct the participant to notify the study site about any new medications he/she takes after the participant was enrolled into the study.

All medications, procedures, and significant non-drug therapies (including physical therapy and blood transfusions) administered after the participant was enrolled into the study must be recorded on the appropriate eCRFs.

Each concomitant drug must be individually assessed against all exclusion criteria and prohibited medication. If in doubt, the Investigator should contact the Novartis medical monitor before enrolling a participant or allowing a new medication to be started. If the participant is already enrolled, contact Novartis to determine if the participant should continue participation in the study.

6.7.1.1 Permitted concomitant therapy requiring caution and/or action

The active metabolites of sacubitril (sacubitrilat) and valsartan are OATP1B1, OATP1B3 and OAT3 substrates; valsartan is also a Multidrug resistance protein 2 (MRP2) substrate. Therefore, co-administration of sacubitril/valsartan with inhibitors of OATP1B1, OATP1B3, OAT3 (e.g. rifampin, cyclosporine) or MPR2 (e.g. ritonavir) may increase the systemic exposure to sacubitrilat or valsartan, respectively. The Investigator should exercise appropriate care when initiating or ending concomitant treatment with such drugs.

The co-administration of sacubitril/valsartan has increased maximum plasma concentration of atorvastatin. These effects may potentially be due to the OATP1B1 and OATP1B3 inhibitory effects of sacubitril. Therefore, caution is recommended when co-administering sacubitril/valsartan with atorvastatin and other statins that are substrates of OATP1B1 and OATP1B3.

Antihypertensive medication should be co-administered with caution due to blood pressure lowering characteristics of the study medication sacubitril/valsartan.

Concomitant use of potassium-sparing diuretics (e.g. spironolactone, triamterene, amiloride), potassium supplements, or salt substitutes containing potassium may lead to increases in serum potassium, if co-medication is considered necessary, monitoring of serum potassium is advised.

In volume depleted patients (including those on diuretic therapy), or patients with compromised renal function, concomitant use of sacubitril/valsartan and Non-steroidal anti-inflammatory drugs (NSAIDs) may lead to an increased risk of worsening of renal function. Therefore, monitoring of renal function is recommended when initiating or modifying treatment in participants on sacubitril/valsartan who are taking NSAIDs concomitantly.

The potential for a drug interaction between sacubitril/valsartan and lithium has not been investigated. Reversible increases in serum lithium concentrations and toxicity have been reported during concomitant administration of lithium with ACEI or ARBs. Therefore, careful monitoring of serum lithium levels is recommended during concomitant use with sacubitril/valsartan.

Guidelines for the management of renal dysfunction, hypotension, and hyperkalemia are provided in Appendix 6, Appendix 8, and Appendix 9, respectively.

6.7.2 Prohibited medication

Use of the treatments displayed in the below table are not allowed while taking study drug due to safety reasons. If the medication included in Table 6-3 is administered, study drug must be discontinued and the actions specified below must be taken.

Table 6-3 Prohibited medication

Medication	Prohibition period	Action taken
any ACEI	36 hours washout period	Discontinue study drug. ACEI must be stopped for 36 hours prior to re-initiation of study drug.
Any ARB		Discontinue study drug. ARB must be stopped for prior to re-initiation of study drug.
Renin inhibitor (aliskiren)		Discontinue study drug. Renin inhibitor must be stopped prior to re-initiation of study drug.

ACEIs, ARBs, and renin inhibitors

The concomitant use of open-label ACEI, ARB, or renin inhibitor is strictly prohibited while the participant is receiving study drug. If the Investigator believes the addition of an ACEI, ARB or renin inhibitor is required, the study drug must be temporarily discontinued. Study drug must be stopped 36 hours prior to starting open-label ACEI. Study drug must be stopped prior to starting open-label ARB or renin inhibitor. Similarly, if study drug is to be restarted, the open-label ACEI must be stopped \geq 36 hours prior to resuming study drug. Open-label ARB or renin inhibitor must be stopped prior to resuming study drug.

6.7.3 Rescue medicine

If in the opinion of the Investigator, the participant does not tolerate the assigned study medication, the Investigator should consider whether non-disease-modifying medication [e.g. calcium channel blockers (CCBs), diuretics, α -blockers] could be adjusted to rectify the situation.

Guidance on handling renal dysfunction, hypotension, and hyperkalemia are provided to Investigators in Appendix 6, Appendix 8, and Appendix 9, respectively.

The Investigator may prescribe any medications and/or supportive care during the study based on clinical needs (excluding use of the prohibited medications described above). Use of rescue medication and/or supportive care must be recorded on the Concomitant medications eCRF.

7 Discontinuation of study treatment and participant discontinuation/withdrawal

7.1 Discontinuation of study treatment

Discontinuation of study treatment for a participant occurs when study treatment is stopped earlier than the protocol planned duration, and can be initiated by either the participant or the Investigator. In this study, if the study treatment is permanently discontinued, the participant

should be discontinued from the study and the end of study visit (Visit EOS) should be conducted (Section 6.4.1).

The Investigator must discontinue study treatment for a given participant if, he/she believes that continuation would negatively impact the participant's well-being.

Study treatment must be discontinued under the following circumstances:

- Participant/guardian decision
- Pregnancy
- Use of prohibited treatment as per recommendations in the prohibited treatment section
- Any situation in which study participation might result in a safety risk to the participant
- Any laboratory abnormalities that in the judgment of the Investigator prevents the participant from continuing participation in the study
- A consecutive 3-month interruption of study treatment

If discontinuation of study treatment occurs, the Investigator should make a reasonable effort to understand the primary reason for the participant's premature discontinuation of study treatment and record this information.

Participants who discontinue study treatment or who decide they do not wish to participate in the study further should NOT be considered withdrawn from the study UNLESS they withdraw their consent (see withdraw of informed consent section).

7.2 Participant discontinuation from the study

Discontinuation from study is when the participant permanently stops receiving the study treatment, and further protocol-required assessments or follow-up, for any reason.

If the participant agrees, a final evaluation at the time of the participant's study discontinuation should be made as detailed in Section 1.3 Schedule of Activities.

7.3 Withdrawal of informed consent and exercise of participants' data privacy rights

Withdrawal of consent/opposition to use of data and/or biological samples occurs in countries where the legal justification to collect and process the data is consent and when a participant:

• Explicitly requests to stop use of their data

and

• No longer wishes to receive study treatment

and

Does not want any further visits or assessments (including further study-related contacts)

This request should be as per local regulations (e.g. in writing) and recorded in the source documentation.

Withdrawal of consent impacts ability to further contact the participant, collect follow-up data (e.g. to respond to data queries) and potentially other country-specific restrictions. It is therefore

very important to ensure accurate recording of withdrawal vs. discontinuation based on the protocol definitions of these terms.

In this situation, the Investigator should make a reasonable effort (e.g. telephone, e-mail, letter) to understand the primary reason for the participant's decision to withdraw their consent/exercise data privacy rights and record this information. The Investigator shall clearly document if the participant has withdrawn his/her consent for the use of data in addition to a study discontinuation.

Study treatment must be discontinued and no further assessments conducted, and the data that would have been collected at subsequent visits will be considered missing.

Further attempts to contact the participant are not allowed unless safety findings require communicating or follow-up.

If the participant agrees, a final evaluation at the time of the participant's withdrawal of consent/exercise data privacy rights should be made as detailed in Section 1.3 Schedule of Activities.

Further details on withdrawal of consent or the exercise of participants' data privacy rights are included in the corresponding informed consent form.

7.4 Lost to follow-up

For participants whose status is unclear because they fail to appear for study visits or fail to respond to any site attempts to contact them without stating an intention to discontinue from study treatment or discontinue from study or withdraw consent (or exercise other participants' data privacy rights), the Investigator must show "due diligence" by documenting in the source documents steps taken to contact the participant, e.g. dates of telephone calls, registered letters, etc. A participant should not be considered as lost to follow-up until due diligence has been completed or until the end of the study.

7.5 Early study termination by the Sponsor

The study can be terminated by Novartis at any time. This may include reasons related to the benefit/ risk assessment of participating in the study, practical reasons (including slow enrollment), or for regulatory or medical reasons.

Reasons for early termination (but not limited to)

- Unexpected, significant, or unacceptable safety risk to participants enrolled in the study
- Decision based on recommendations from applicable board(s) after review of safety and efficacy data
- Discontinuation of study treatment development in this indication

In taking the decision to terminate, Novartis will always consider participant welfare and safety. Should early termination be necessary, participants must be seen as soon as possible and treated as a participant who discontinued from study treatment. The Investigator must provide follow-up medical care for all patients who are prematurely withdrawn from study drug or refer them for appropriate ongoing care. The Investigator may be informed of additional procedures to be followed in order to ensure that adequate consideration is given to the protection of the

participant's interests. The Investigator or Novartis depending on local regulation will be responsible for informing Institutional Review Boards (IRBs) / Independent Ethics Committees (IECs) of the early termination of the trial.

8 Study Assessments and Procedures

After identifying a potential participant, an ICF and assent (if applicable) must be signed by the parent(s)/legal guardian(s) and by the participant (as applicable) before performing any study-related procedures that are not considered standard of care for pediatric HF participants at that site. Procedures that are part of a site's standard of care for a pediatric participant or that were done as part of the End of Study visit (Visit 599) of PANORAMA-HF OLE study may pre-date the signed ICF for this study. The AE and SAE reporting period will begin at the time the ICF is signed.

The Assessment Schedule (Table 1-2) lists all of the assessments when they are performed. All data obtained from these assessments must be supported in the participant's source documentation. The "X" in the table denotes the assessments to be recorded in the clinical database or received electronically from a vendor. The "S" in the table denotes the assessments that are only in the participant's source documentation and do not need to be recorded in the clinical database.

Sacubitril/valsartan treatment will start at Visit Day1, which is the same day as the End of Study visit (Visit 599) of PANORAMA-HF OLE study. The data of some assessments (such as vital sign, height, and weight) at the End of Study visit (Visit 599) in PANORAMA-HF OLE study will be utilized as the data at Visit Day1 for this study.

A telephone visit (Visit M3) and an on-site visit (Visit M6) will occur 3 months and 6 months after Visit Day1, respectively. The visits as same Visit M3 and Visit M6 will then be repeated every 3 months until the end of the study. When the pediatric formulation of sacubitril/valsartan becomes available in Japan, or this study is terminated by Novartis, any participants should return to the study site as soon as possible for End of Study (EOS) visit (Visit EOS) regardless of subsequent scheduled visit, and all of the assessments listed for Visit EOS will be performed.

Participants should take their scheduled dose of sacubitril/valsartan in the morning of their study visits. Participants are not required to fast overnight on the day prior to or the day of the study visit.

Participants, who discontinue sacubitril/valsartan for 3 consecutive months, will be discontinued from the study and are to attend Visit EOS.

Participants should be seen for all visits/assessments as outlined in the assessment schedule or as close to the designated day/time as possible. If one visit is postponed or brought forward, it should not result in the next visit being postponed or brought forward. The next visit, if at all possible, should adhere to the original schedule in relation to Visit Day1. Missed or rescheduled visits should not lead to automatic discontinuation. Specific circumstances surrounding missed or rescheduled visits must be discussed with the study monitor. Participants who prematurely discontinue the study treatment, or prematurely withdraws from the study for any reason should be scheduled for a final visit as soon as possible, at which time all of the assessments listed for the final visit (Visit EOS) will be performed. At this final visit, all dispensed investigational

product should be reconciled, and the adverse event and concomitant medications recorded on the eCRF.

As per Section 4.5, during a public health emergency as declared by local or regional authorities i.e. pandemic, epidemic or natural disaster that limits or prevents on-site study visits, alternative methods of providing continuing care may be implemented by the Investigator as the situation dictates. If allowable by a local health authority, national and local regulations and depending on operational capabilities, phone calls, virtual contacts (e.g. tele consultation) or visits by site staff/ off-site healthcare professional(s) staff to the participant's home, can replace on-site study visits, for the duration of the disruption until it is safe for the participant to visit the site again. If the Investigator delegates tasks to an off-site healthcare professional, the Investigator must ensure the individual(s) is/are qualified and appropriately trained to perform assigned duties. The Investigator must oversee their conduct and remain responsible for the evaluation of the data collected.

8.1 Screening

Participants or parents/guardians who sign an informed consent form for themselves or for their child, respectively, will be screened. The inclusion/exclusion criteria at Visit Day1 will be checked.

8.2 Participant demographics/other baseline characteristics

Participant demographic and baseline characteristic data at Visit Day1 will be collected including: year of birth (where allowed) age in years (age in months for participants < 2 years, where allowed), sex, race and ethnicity, as well as the Identification Number (ID No.). Additionally, pediatric heart failure history, vital signs, weight and height will be collected. Relevant medical history/current medical condition data includes data until the start of study drug. HF medications will be recorded on the Concomitant Medications eCRF.

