5.3 Screen failures

Participants or parents/guardians who sign an informed consent form for themselves or for their child, respectively, and who (i.e. the participant) are subsequently found to be ineligible for this study, will be considered a screen failure. The reason for screen failure should be entered on the applicable electronic Case Report Form (eCRF). The baseline characteristics at Visit Day1, demographic information, informed consent, and Inclusion/Exclusion pages must also be completed for screen failure participants. No other data will be entered into the clinical database for participants who are screen failures, unless the participant experienced a serious adverse event (SAE) during the screening phase (see SAE section for reporting details).

Participants or parents/guardians who sign an informed consent for themselves or for their child, respectively, and who are considered eligible but fail to be started on treatment on Visit Day1 for any reason may be enrolled in this study. However, they will have to discontinue the study unless the study treatment starts within 3 months from Visit Day1 and will be considered an early study termination. The reason for early study termination should be captured on the appropriate disposition eCRF at Visit EOS.

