8.4.1 Physical examinations

A complete physical examination will include the examination of general appearance, skin, neck (including thyroid), eyes, ears, nose, throat, lungs, heart, abdomen, back, lymph nodes, extremities, vascular, and neurological. If indicated based on medical history and/or symptoms, rectal, external genitalia, breast, and pelvic exams will be performed.

Information for all physical examinations must be included in the source documentation at the study site. Clinically relevant findings that are present prior to signing informed consent must be recorded on the appropriate eCRF that captures medical history. Significant findings made after signing informed consent which meet the definition of an Adverse Event must be recorded as an adverse event.

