8.6.1 Adverse events

An AE is any untoward medical occurrence (e.g. any unfavorable and unintended sign [including abnormal laboratory findings], symptom or disease) in a clinical investigation participant after providing written informed consent for participation in the study. Therefore, an AE may or may not be temporally or causally associated with the use of a medicinal (investigational) product.

The Investigator has the responsibility for managing the safety of individual participant and identifying adverse events.

Novartis qualified medical personnel will be readily available to advise on trial-related medical questions or problems.

The occurrence of adverse events must be sought by non-directive questioning of the participant at each visit during the study. Adverse events also may be detected when they are volunteered by the participant during or between visits or through physical examination findings, laboratory test findings, or other assessments.

Adverse events must be recorded under the signs, symptoms, or diagnosis associated with them, accompanied by the following information (as far as possible) (if the event is serious refer to Section 8.6.2):

- 1. The severity grade
- mild: usually transient in nature and generally not interfering with normal activities
- moderate: sufficiently discomforting to interfere with normal activities
- severe: prevents normal activities
- 2. Its relationship to the study treatment and other investigational treatment. If the event is due to lack of efficacy or progression of underlying illness (i.e. progression of the study indication) the assessment of causality will usually be 'Not suspected.' The rationale for this guidance is that the symptoms of a lack of efficacy or progression of underlying illness are not caused by the trial drug, they happen in spite of its administration and/or both lack of efficacy and progression of underlying disease can only be evaluated meaningfully by an analysis of cohorts, not on a single participant
- 3. Its duration (start and end dates or ongoing) and the outcome must be reported
- 4. Whether it constitutes a SAE (see Section 8.6.2 for definition of SAE) and which seriousness criteria have been met
- 5. Action taken regarding with study treatment.

All adverse events must be treated appropriately. Treatment may include one or more of the following:

- Dose not changed
- Dose Reduced/increased
- Drug interrupted/permanently discontinued
- 6 Its outcome

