Conditions that were already present at the time of informed consent should be recorded in medical history of the participant.

Adverse events (including lab abnormalities that constitute AEs) should be described using a diagnosis whenever possible, rather than individual underlying signs and symptoms.

Adverse event monitoring should be continued for at least 30 days following the last dose of study treatment.

Once an adverse event is detected, it must be followed until its resolution or until it is judged to be not recovered/not resolved (e.g. continuing at the end of the study), and assessment must be

made at each visit (or more frequently, if necessary) of any changes in severity, the suspected relationship to the interventions required to treat it, and the outcome.

Information about adverse drug reactions for the investigational drug can be found in the IB.

Abnormal laboratory values or test results constitute adverse events only if they fulfill at least one of the following criteria:

- they induce clinical signs or symptoms
- they are considered clinically significant
- they require therapy

Clinically significant abnormal laboratory values or test results must be identified through a review of values outside of normal ranges/clinically notable ranges, significant changes from baseline or the previous visit, or values which are considered to be non-typical in participant with the underlying disease. Alert ranges for laboratory and other test abnormalities are included in Section 10.3.

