9.3.1 Definition of primary endpoint(s)

Any adverse events (treatment emergent or not) are considered primary endpoints.

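### Protocol 8.2 runs medical history to the start of study drug, while Sections 8, 8.4.1 and 8.6.1 set the history/AE boundary at consent; for late starters the two rules overlap by up to 3 months.

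*Protocol*

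**What the plan says.** The boundary between medical history and adverse events is stated in several places in the protocol.

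- **Section 8.2 (baseline characteristics):** "Relevant medical history/current medical condition data includes data until the start of study drug".
- **Section 8 (opening text):** "The AE and SAE reporting period will begin at the time the ICF is signed".
- **Section 8.4.1 (physical examinations):** "Clinically relevant findings that are present prior to signing informed consent must be recorded on the appropriate eCRF that captures medical history", and then "Significant findings made after signing informed consent which meet the definition of an Adverse Event must be recorded as an adverse event".
- **Section 8.6.1 (adverse events):** an AE is an untoward occurrence "in a clinical investigation participant after providing written informed consent for participation in the study". The same section adds: "Conditions that were already present at the time of informed consent should be recorded in medical history of the participant".

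Two further provisions make the difference matter. Section 5.3 lets an eligible, consented participant who does not start on Visit Day1 stay enrolled, with the limit that "they will have to discontinue the study unless the study treatment starts within 3 months from Visit Day1". Section 9.3.1 defines the primary endpoint broadly: "Any adverse events (treatment emergent or not) are considered primary endpoints".

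**The concern.** Section 8.2 uses first dose as the cut-off; the other sections use consent. Nothing in the protocol or the SAP says which prevails, and the SAP has no rule for separating history from AEs.

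For someone who consents on Visit Day1 and starts drug weeks later, a new non-serious condition in the interval fits both descriptions. One site could enter it as history, another as an AE, and a third on both forms. Because non-treatment-emergent AEs are part of the primary endpoint, an event entered only as history is missing from the primary table. It would also appear in the wrong place, since Protocol 9.2.2 and SAP 2.3.2 tabulate medical history at Visit Day1 by system organ class and preferred term.

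**Working it through.** The plan gives no figure to reproduce. Protocol 9.9.1 states a cap of 8 patients and no required sample size, and Protocol 9.3.2 has no hypothesis to test. The check is a comparison of texts plus simple arithmetic.

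**1. Length of the overlap.** Overlap = date of first dose minus date of consent.
- Protocol 9.2.1 and SAP 2.1.1 date consent to Visit Day 1.
- A participant dosed on Visit Day1 has an overlap of about 0 days.
- The latest start under Section 5.3 is Visit Day1 plus 3 months. Three calendar months run from 89 to 92 days, depending on the start month. With the SAP's day 91 for Visit M3, the figure is 91 − 1 = 90 days.

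**2. How one event in that interval is classified** (non-serious, new onset after consent, before first dose).

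| Text | Classification |
|---|---|
| Protocol 8.2 | medical history |
| Protocol 8, 8.4.1, 8.6.1 | adverse event |
| Protocol 9.3.1, SAP 2.5.1 | primary endpoint, if recorded as an AE |
| SAP 2.7.1 | not treatment emergent, because for a late starter TEAEs begin at first dose |

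**3. When history is taken.** Table 1-2, footnote 1, moves the Visit Day1 assessments to the treatment-start visit for participants whose drug was interrupted at Visit 599. Medical history is one of those assessments. The site may therefore be taking history up to 3 months after consent, at a visit where 8.2 tells it to include everything up to that day. AEs are collected at the same visit.

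**4. Effect on a table row.** SAP 2.5.2 uses the Safety Set for the primary endpoint, so only late starters who are later dosed count. If one of n such patients has an event filed only as history and no other AE of that term, the row for that term falls by 1/n:
- n = 8: 1/8 = 12.5 percentage points
- n = 5: 1/5 = 20 percentage points

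For the overall any-AE row to move by the same amount, the patient must have no other AE at all.

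**5. What is not affected.**
- Section 8.6.3 requires every SAE after consent to be reported within 24 hours, whatever 8.2 says about history.
- Under the SAP definition, TEAE, treatment-emergent SAE and special-interest tables start at first dose for late starters, so events before that dose are outside them. The footnote to Protocol 9.6 dates TEAEs from Visit Day 1 without this exception; the statement here rests on the SAP rule.

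**The case against.** The strongest reply is that 8.2 describes what history includes. It does not say that such conditions go only there, and it exempts nothing from AE reporting. Section 8.4.1 makes recording of qualifying post-consent findings mandatory, and Section 8.4 refers the reader to 8.6 for AE collection. A site could satisfy every sentence by using both forms, and an AE is lost only if the site lets 8.2 override the mandatory text. The analysis sections also fix history and baseline at Visit Day1, not at first dose. This stands, and it limits the point to a possible misfiling. It does not remove the conflict: entry on both forms still puts a post-consent event in the baseline table, and 8.4.1 and 8.6.1 define history by consent.

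It can also be argued that footnote 1 moves consent, a Day1 item, to the treatment-start visit, which would close the gap for interrupted participants. Section 5.3 (consented but not started on Visit Day1) and the study-period definition point the other way.

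A reader might go further and infer that up to 3 months of primary-endpoint events will be lost, or that participants entering off drug are the ones most likely to have events. The documents support neither. They give no number of late starters, which may be zero, and no event rates.

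Nor can an assumed rate be turned into the chance of a 12.5-point shift in the overall row. At 1, 2 or 4 AEs per patient-year (assumed), the chance of at least one AE in 3 months is 1 − exp(−0.25 × rate) = 22%, 39% or 63%. The overall shift also needs no later AE. With an assumed 12 months of later follow-up, multiplying by exp(−rate) gives 8%, 5% and 1%. With 6 months, multiplying by exp(−0.5 × rate) gives 13%, 14% and 9%. All of these still presuppose a late starter and a site that files the event only as history.

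**Conclusion.** The protocol contradicts itself on where medical history ends, and 8.2 is the section out of line. The consequence is narrow. A non-serious event between consent and first dose, in a late starter who is later dosed, may be missing from the primary summary or wrongly shown as baseline history. The window is about 0 days for same-day starters and at most 3 months otherwise. Each affected patient with no other AE of that term moves that row by 1/n, which is 12.5 points if all 8 places are filled and treated, and more with fewer patients.

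The total effect cannot be computed, because the number of late starters is not given. The conclusion assumes that consent is dated to Visit Day 1, as Protocol 9.2.1 states, and that the SAP's TEAE rule is applied. Correction is warranted because the rule bears on capture of the primary endpoint, not because a loss has been shown.

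**What to change.** In Protocol 8.2, change the end of the medical-history period from start of study drug to *the signing of informed consent for this study*, matching 8.4.1 and 8.6.1. Add one sentence stating that events with onset after consent and before first dose are recorded on the AE page as non-treatment-emergent AEs. The overlap then falls from at most 3 months to 0 days.

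The cost is a short text change and a note to sites, with no new visits or data. A check of medical-history onset dates against the consent date before database lock is optional. It would find any event already misfiled, but the documents do not show whether the existing automatic discrepancy checks (Protocol 10.1.5.1) already cover it.
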